6.6. Study Drug Stopping Rules

6.6.1. Adverse Reaction Rules

An adverse reaction is any TEAE that is considered related to the study medication (for a full definition of related TEAEs, see Section 10.3.5).

Any TEAEs or TESAEs that are not considered related to study drug do not constitute adverse reactions or serious adverse reactions and, therefore, these rules do not apply.

6.6.1.1. General Adverse Reaction rules

The general adverse reaction rules refer to all adverse reactions, excluding those relating to the liver and hematology and QT interval prolongation. The CTCAE may not give clear enough guidance, and grading may not be appropriate for this study in healthy volunteers; therefore, special study-specific rules have been created.

Individual Adverse Reaction Rules

An individual subject will not receive the dose of ALXN1840 in the subsequent period, if either of the following occurs:

• Subject experiences any CTCAE Grade 3 (or higher) adverse reaction, or a serious adverse reaction, irrespective of severity/CTCAE grade.

• Subject experiences any CTCAE Grade 1 or 2 adverse reaction considered to be related to study drug that is considered a safety concern by the Safety Review Committee.

Group Adverse Reaction Rules

Dosing will be suspended for all subjects, or potentially only in an affected cohort, if either of the following occurs:

- One subject (among any of the 48 total subjects) experiences a non-serious, severe (CTCAE Grade 3) adverse reaction.
- One subject experiences a serious adverse reaction, irrespective of severity/CTCAE grade.

In the event of suspension of dosing, continuation of the study will require a protocol amendment that has been approved by the MHRA and ethics committee.

Special individual Adverse Reaction Rules

Dosing in an individual subject will be suspended if they experience any of the following:

- Liver function test elevation
 - ALT or AST value $> 3 \times ULN$ together with bilirubin increase $> 2 \times ULN$.
 - ALT or AST value $> 8 \times ULN$.
 - ALT or AST value $> 3 \times ULN$, and symptomatic.
- Hematology
 - Hemoglobin reduction to an absolute value of 8g/dL (80g/L) or lower.
 - Platelet count reduction of > 50% from baseline or absolute value < 80.000/mm³ (Day -1 blood samples).
- QT interval prolongation
 - A prolongation of the uncorrected QT interval of > 500ms (using consistent, technically valid triplicate ECG).

Special group AR rules

If 1 subject fulfils the special individual adverse reaction rules, and this could be reasonably attributed to study drug, a Safety Review Committee meeting will be arranged and, if necessary, dosing for all subjects will be temporarily suspended until the Safety Review Committee meets. At this meeting, a decision will be made regarding the continuation of dosing in the remaining subjects.

If it is then confirmed that 1 subject fulfils Hy's Law criteria, dosing will be suspended in all subjects and can only continue with a substantial amendment to the protocol that has been approved by the MHRA and ethics committee.

If 2 or more subjects fulfil any of the other special individual adverse reaction rules, dosing will be suspended in all subjects and can only continue if the Safety Review Committee decides that dosing can continue, and a substantial amendment is made to the protocol that is approved by the MHRA and ethics committee.

Details of the Safety Review Committee are provided in Section 8.4.

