10.3.5. Recording and Follow-Up of AEs and/or SAEs

Adverse Event and Serious Adverse Event Recording

- When an AE or SAE occurs, it is the responsibility of the Investigator to review all documentation (eg, hospital progress notes, laboratory reports, and diagnostics reports) related to the event.
- The Investigator will then record all relevant AE or SAE information in the CRF.
- It is not acceptable for the Investigator to send photocopies of the subject's medical records to the Sponsor or designee in lieu of completion of the AE/SAE CRF page.
- There may be instances when copies of medical records for certain cases are requested by the Sponsor or designee. In this case, all subject identifiers, with the exception of the subject number, will be redacted on the copies of the medical records before submission.
- The Investigator will attempt to establish a diagnosis of the event based on signs, symptoms, and/or other clinical information. Whenever possible, the diagnosis (not the individual signs/symptoms) will be documented as the AE/SAE.

Assessment of Event Severity

The Investigator will make an assessment of intensity for each AE and SAE reported during the study and assign it to 1 of the following categories from CTCAE v5.0, published 27 Nov 2017. Each CTCAE term is a Lowest Level Term per MedDRA. Each Lowest Level Term will be coded to a MedDRA Preferred Term:

- 1. Grade 1: Mild (asymptomatic or mild symptoms; clinical or diagnostic observations only; intervention not indicated)
- 2. Grade 2: Moderate (minimal, local or noninvasive intervention indicated; limiting age-appropriate instrumental activities of daily living [ADL])
- 3. Grade 3: Severe (severe or medically significant, but not immediately life-threatening; hospitalization or prolongation of hospitalization indicated; disabling; limiting self-care ADL)
- 4. Grade 4: Life-threatening consequences; urgent intervention indicated
- 5. Grade 5: Death related to AE

Any change in the severity of an AE should be documented based on specific guidelines in the CRF Completion Guidelines.

Severity and seriousness must be differentiated: severity describes the intensity of an AE, while the term seriousness refers to an AE that has met specific criteria for an SAE as described above.

Causality Assessment

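### The group stopping rule in Protocol 6.6.1.1 leaves a non-serious Grade 4 reaction unnamed and allows suspension of a cohort that the design does not define

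*Protocol*

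**What the plan says.** The stopping rules are in Protocol Section 6.6.1.1 and apply only to adverse reactions, which Section 6.6.1 defines as treatment-emergent events considered related to study drug. Liver, hematology and QT findings are handled by separate special rules: "The general adverse reaction rules refer to all adverse reactions, excluding those relating to the liver and hematology and QT interval prolongation".

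The individual rule withholds the next period's dose in either of two situations. The relevant one is "Subject experiences any CTCAE Grade 3 (or higher) adverse reaction, or a serious adverse reaction, irrespective of severity/CTCAE grade". The other concerns Grade 1 or 2 reactions that the Safety Review Committee regards as a safety concern.

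The group rule opens with "Dosing will be suspended for all subjects, or potentially only in an affected cohort, if either of the following occurs". It has two triggers:

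- The first is tied to a single grade: "One subject (among any of the 48 total subjects) experiences a non-serious, severe (CTCAE Grade 3) adverse reaction".
- The second depends on seriousness and sets no grade: "One subject experiences a serious adverse reaction, irrespective of severity/CTCAE grade".

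The sentence after them reads "In the event of suspension of dosing, continuation of the study will require a protocol amendment", and goes on to require approval by the regulator and the ethics committee.

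Section 10.3.5 supplies the grade definitions, including "Grade 4: Life-threatening consequences; urgent intervention indicated", and adds "Severity and seriousness must be differentiated: severity describes the intensity of an AE".

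**The concern.** A group stopping rule protects subjects who have not yet been dosed. It has to be applied quickly, so its wording should settle what happens without interpretation. Two features of this one do not.

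First, the individual rule has an open-ended grade range and the non-serious group trigger has a single grade. Read literally, the group rule is not monotone in severity: a non-serious Grade 3 reaction suspends dosing, while a non-serious Grade 4 reaction does not.

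Second, the extent of a suspension depends on a term that nothing in the protocol defines. The possibility of a partial suspension also conflicts with the sentence on amendments that follows it.

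At stake is whether the investigator, the sponsor and the Safety Review Committee would reach the same decision on the same event.

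**Working it through.** No arithmetic drives this point. The check sets each combination of grade and seriousness against the rules.

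**Grade range.** All rows are related reactions outside the liver, hematology and QT exclusions.

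| Reaction | Individual rule | Group trigger 1 (non-serious Grade 3) | Group trigger 2 (serious) |
|---|---|---|---|
| Non-serious, Grade 1 or 2 | Only if the committee sees a safety concern | No | No |
| Non-serious, Grade 3 | Yes | Yes | No |
| Non-serious, Grade 4 | Yes | No | No |
| Serious, any grade | Yes | No | Yes |

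A non-serious Grade 5 reaction cannot occur, because Grade 5 is death (Section 10.3.5) and death is the first seriousness criterion (Section 10.3.3). The non-serious Grade 4 row is therefore the only one in which the individual rule always fires and the group rule does not.

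**How nearly empty that row is.** Grade 4 is described by life-threatening consequences, and a life-threatening event is serious. Most Grade 4 reactions will therefore meet trigger 2. The definitions do not close the row completely, for two reasons. Section 10.3.3 limits life-threatening to an actual risk of death at the time of the event and excludes hypothetical risk. Section 10.3.5 requires severity and seriousness to be judged separately. The documents do not say how often the two would diverge.

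**Reach.** In that row the individual rule acts on 1 subject. The other 48 − 1 = 47 planned subjects are under no stated group trigger for that event. This is an upper limit, since some of them may already have completed dosing.

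**Whether the Safety Review Committee closes the row.** Section 8.4 requires a meeting within 24 hours of a serious treatment-emergent event, or of the withdrawal of any subject due to an adverse reaction. Its task is to determine whether a group rule applies and what this means for continuation. For a non-serious Grade 4 reaction, the literal answer to the first question is that none applies. If the reaction occurs in Period 2, the individual rule has no later dose to withhold and no withdrawal need follow. In that case only the optional ad hoc meeting remains.

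**Cohort wording.** Section 4.1 describes a single-center crossover with two sequences of 24 subjects, each subject receiving both treatments. It defines no cohort. A cohort could be read as a sequence, a period or a group dosed together, and the protocol gives no criterion for choosing among these or for limiting a suspension at all. The phrase governs both group triggers, including the serious one.

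**Partial suspension against the amendment sentence.** A partial suspension implies that dosing continues in the remaining subjects. The next sentence makes continuation of the study after a suspension depend on an approved amendment and states no exception. If that sentence applies to every suspension, the partial option has no clear practical effect before approval. If it applies only to a full suspension, the text does not say so. The special group rules in the same section refer only to all subjects, so they do not share this difficulty.

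**The case against.** The strongest objection is that the gap has almost no practical content. Deaths and life-threatening reactions are serious and trigger the group rule. The laboratory effects that the protocol identifies in liver and blood are covered by special rules. A laboratory value becomes an adverse event only if the investigator judges it clinically significant. Several safeguards sit behind the rule: the committee (Section 8.4), immediate discussion of safety concerns with the medical monitor (Section 8), and termination for unacceptable risk (Section 5.4.1). Prior experience is also reassuring. Section 2.2 reports 39 + 21 = 60 adverse events in 18 + 18 = 36 healthy subjects given 60 mg, which is 60/15 = 4 times the dose here. Of these events, 38 + 21 = 59 were Grade 1, one was Grade 2, and none was serious. All of this stands, and it is why the point is minor. It does not make the two grade ranges agree, and none of the safeguards is a stated group trigger.

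Four stronger readings are tempting, and the documents do not support them.

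- A reader might infer that the group rule covers only Grade 3, so that a fatal or life-threatening reaction would stop one subject and not the study. The second trigger covers any serious reaction of any grade.
- A reader might point to creatine phosphokinase or electrolytes as values that reach Grade 4 without being serious. That depends on numerical CTCAE thresholds that neither document gives.
- A reader might expect different sites to act differently. There is one site; any disagreement would be among the investigator, the sponsor and the committee.
- A reader might conclude that the cohort wording lets dosing continue freely after a serious reaction. The default is suspension for all subjects, and the amendment sentence carries no exception.

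**Conclusion.** The point holds as a minor internal inconsistency. One combination, a related Grade 4 reaction judged non-serious, is caught by the individual rule and named by neither group trigger, although the less severe Grade 3 reaction is. Separately, the group rule offers a partial suspension in terms of a unit that this design does not have, and does not square it with the amendment requirement.

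The conclusion assumes that the triggers are applied literally and that grade and seriousness are assigned separately, as Section 10.3.5 requires. How often the gap would matter cannot be estimated from the documents; the grade and seriousness definitions and the earlier healthy-volunteer data both suggest rarely. The primary bioavailability analysis is unaffected unless a suspension actually occurs.

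**What to change.** Make two wording changes in Protocol Section 6.6.1.1, by amendment:

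1. Reconcile the grade range of the group rule with that of the individual rule, so that no grade falls between the two group triggers.
2. Either remove the reference to an affected cohort or define it in terms of this design. If it is kept, state when a suspension may be partial and reconcile that option with the requirement for an approved amendment.

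The clinical thresholds are for the sponsor to decide, and none is proposed here. No new data, assessments or analyses are needed. The downside is that a study-wide pause becomes marginally more likely.

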8.2.3. Electrocardiograms

8.2.3.1. Recording of 12-Lead ECGs

A triplicate 12-lead ECG will be obtained using a GE Marquette MAC1200® / MAC1200ST® recorder connected via a fixed network connection to the MUSE® Cardiology Information System (MUSE) after the subject has been resting for at least 10 minutes. 12-lead ECGs will be conducted before PK/PD/biomarker blood sampling if these 2 events occur at the same time. The timing of 12-lead ECGs is described in the Schedule of Activities (Table 1 and Table 2).

12-lead ECGs recorded during screening will be stored electronically on the MUSE information system. Only ECGs recorded electronically will be valid ECGs for any purpose other than safety assessment. ECG printouts may be filed in the subject's case report form (CRF) for medical safety reviews.

Each 12-lead ECG recorder will be set up to the required technical specifications and containing the information required to identify the records. Each ECG recording will be clearly identified (Subject ID, visit date, and the actual times of ECG recordings).

12-lead ECG recordings will be made after the subjects have been resting in a supine position for at least 10 minutes. The subjects will avoid postural changes during the ECG recordings and clinical staff will ensure that subjects are awake during the ECG recording.

At each time point, the 12-lead ECG will be recorded in triplicate, to reduce variance and improve the precision of measurement. The triplicates will be performed at approximately 1-minute intervals. Each ECG recording (trace) will last 10 seconds. Repeat ECGs will be performed until at least three 10-second ECG records per scheduled time-point meet the quality criteria set out in the Study Operations Manual and the applicable Standard Operating Procedure to enable reading and analyzing at least 5 complexes per derivation.

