8.2.3.2. Safety Review of 12-Lead ECGs

All recorded 12-lead ECGs will be reviewed by the Investigator, or qualified designee, and the review findings will be documented in the CRF. If a subject shows an abnormal ECG, additional safety recordings (including the use of 5- or 12-lead Holter equipment) may be made and the abnormality be followed to resolution, if required.

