9.4.2. Safety Analyses

All safety analyses will be performed on the Safety Set.

Safety analyses will include an analysis of all AEs, ECGs, clinical laboratory data, physical examinations, and vital sign measurements using descriptive statistics. No inferential statistical analyses are planned on the safety parameters of this study. The incidence of AEs and SAEs will be summarized, by System Organ Class (SOC) and Preferred Term for each treatment and overall, by relationship to study drug. Adverse events will also be summarized by treatment and overall by severity. Serious AEs and AEs resulting in withdrawal from the study will be listed. Subjects having multiple AEs within a category (eg, overall, SOC, Preferred Term) will be counted once in that category. For severity tables, a subject's most severe event within a category will be counted.

Changes from baseline in vital sign measurements and laboratory assessments (eg, chemistry, cell blood count with differential, and urinalysis) will be summarized by treatment. Laboratory parameter values will be graded according to the National Cancer Institute Common Terminology Criteria for Adverse Events (CTCAE). Shift tables by treatment will be produced for these laboratory parameters. These tables will summarize the number of subjects with each baseline grade relative to the reference ranges and changes to the worst highest grade assessed post-dose during the study.

The ECG parameters will be measured at the specified time points, including heart rate, PR, RR, QRS, QT, and corrected QTcF intervals. The average of the triplicate ECG readings at the time points collected will be calculated, and changes from pretreatment baseline values will be assessed by each treatment.

All concomitant medications will be coded and summarized using the WHO Drug Dictionary.

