4.11.3 Electrocardiograms

ECG parameters will be measured at the time points specified in the study protocol and will at least include heart rate, PR interval, RR interval, QRS duration, interval between the start of the Q wave and the end of the T wave in an ECG (QT), and corrected QT interval corrected using Fridericia's formula (QTcF), where QTcF=QT/RR^1/3. The variables will be listed individually.

Three or more replicate measurements are taken at each protocol time point and the arithmetic mean of the evaluable/available measurements will be taken as the measurement to be used for summary statistics. Arithmetic mean values will also be included into the listings.

For ECG variables, the change from baseline will be derived using the arithmetic mean value of each time-point triplicate minus the arithmetic mean of baseline triplicate values per period.

Mean absolute (observed) values and corresponding changes from baseline in the ECG variables will be summarized by treatment and time point.

An outlier analysis will be performed on mean values that will summarize the frequency and percentage of subjects who meet any of the following outlier criteria at each visit by treatment:

- QT, QTcF interval > 450 msec to ≤ 480 msec
- QT, QTcF interval > 480 msec to ≤ 500 msec
- QT, QTcF interval > 500 msec

- QT, QTcF interval increases from baseline > 30 msec to ≤ 60 msec
- QT, QTcF interval increases from baseline > 60 msec

As per the clinical study protocol, recorded ECGs will be reviewed by the Investigator, or qualified designee, and abnormal ECGs may be followed by additional safety recordings. For summary analyses, the additional safety ECGs will be used only, and will replace the initial ECGs that were reviewed as abnormal.

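### The only QT stopping criterion uses uncorrected QT, so a drug-related QTcF above 500 ms at a heart rate above 60/min can meet no rule in Protocol 6.6

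*Protocol*

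**What the plan says.** Protocol 6.6.1.1 has two layers. The general rules act on reactions of Grade 3 or higher, on serious reactions, and on Grade 1 or 2 reactions that the Safety Review Committee regards as a safety concern. Their scope is limited: "The general adverse reaction rules refer to all adverse reactions, excluding those relating to the liver and hematology and QT interval prolongation".

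The special individual rules cover the three excluded areas. For QT there is a single criterion: "A prolongation of the uncorrected QT interval of > 500ms (using consistent, technically valid triplicate ECG". There is no limit on QTcF and none on change from baseline.

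The special group rules build on the individual ones. One subject who fulfils a special individual rule, with reasonable attribution to study drug, leads to a Safety Review Committee meeting. Beyond that, "If 2 or more subjects fulfil any of the other special individual adverse reaction rules, dosing will be suspended in all subjects", and dosing resumes only with the committee's decision and an approved substantial amendment.

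QTcF is planned elsewhere. Protocol 9.4.2 names the ECG parameters, "including heart rate, PR, RR, QRS, QT, and corrected QTcF intervals". SAP 4.11.3 gives the correction ("where QTcF=QT/RR^1/3") and has one top outlier category for both measures: "QT, QTcF interval > 500 msec".

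**The concern.** Uncorrected QT shortens as heart rate rises, so a fixed limit on it corresponds to a different corrected interval at each rate. Above 60/min, a subject could fall in the SAP's highest QTcF category while meeting no dosing rule. Because QT prolongation is outside the general rules, Grade 3 or seriousness does not bring the event back under Section 6.6.

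Three things would then not happen by rule:

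- The subject would not be held back from the Period 2 dose.
- The one-subject Safety Review Committee meeting would not be called.
- The subject would not count towards the two-subject suspension.

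**Working it through.** **Rule trace for a drug-related event with QTcF above 500 ms and QT at or below 500 ms**

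| Rule in Protocol 6.6.1.1 | Met? | Reason |
|---|---|---|
| General individual rules | No | QT prolongation is outside their scope |
| General group rules | No | Same scope limit |
| Special individual rule, QT | No | QT is not above 500 ms |
| Special group rule, one subject | No | Needs a special individual rule to be met |
| Special group rule, two or more subjects | No | Same |

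A separate related event, such as syncope, could still be judged under the general rules. A QTcF above 500 ms with QT also above 500 ms does meet the special rule.

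**Where the two measures part**

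Input: the formula in SAP 4.11.3, with RR taken in seconds, so RR = 60/HR.

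QTcF = QT / (60/HR)^(1/3)

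At 60/min, RR = 1 and QT = QTcF. That is the exact crossover.

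QTcF when QT is exactly 500 ms (rule not yet met):

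| HR (/min) | 50 | 55 | 60 | 65 | 70 | 80 |
|---|---|---|---|---|---|---|
| QTcF (ms) | 470.5 | 485.7 | 500.0 | 513.5 | 526.4 | 550.3 |

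The missed band is therefore empty at 60/min or below, 500 to 526 ms at 70/min and 500 to 550 ms at 80/min. For example, a QT of 480 ms at 70/min gives a QTcF of 505.3 ms and no rule is met. Below 60/min the rule acts early, at a QTcF of about 470 ms at 50/min. Between 50 and 80/min the same limit spans 550.3 − 470.5 = 79.8 ms of corrected interval.

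The heart rate at or above which a given QTcF is missed is HR = 60 × (QTcF/500)^3:

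| QTcF (ms) | 505 | 510 | 520 | 530 | 550 |
|---|---|---|---|---|---|
| HR (/min) | 61.8 | 63.7 | 67.5 | 71.5 | 79.9 |

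These cutoffs need no heart-rate distribution. The documents give none; they say only that "12-lead ECG recordings will be made after the subjects have been resting in a supine position for at least 10 minutes".

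**How many ECGs matter**

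From Protocol Tables 1 and 2, the scheduled ECGs after the first dose are at 4, 24 and 96 h in each of two periods, before the Period 2 dose, and at end of study: 3 + 3 + 1 + 1 = 8 per subject, and 48 × 8 = 384. Four of these fall before the Period 2 dose and could change the subject's own dosing: 48 × 4 = 192.

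**Extra triggers if QTcF is added**

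Assumptions, none of them in the documents: QTcF normal with mean 400 to 420 ms and SD 20 or 25 ms; heart rate normal and independent of QTcF, mean 55 to 70/min, SD 10. These describe background readings without a drug effect.

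Expected extra readings = n × Σ over HR > 60 of w(HR) × [P(QTcF > 500) − P(QTcF > 500/(60/HR)^(1/3))]

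| n | QTcF SD 20 ms | QTcF SD 25 ms |
|---|---|---|
| 384 | 0.00003 to 0.0097 | 0.0030 to 0.203 |
| 192 (half of the above) | 0.000015 to 0.0049 | 0.0015 to 0.10 |

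The low end of each range is QTcF mean 400 with heart-rate mean 55; the high end is 420 with 70. As a check on the largest value, (500 − 420)/25 = 3.2 SD has an upper tail of about 0.00069, and 384 × 0.00069 = 0.26 readings above 500 ms at any heart rate. The 0.203 is the part of these with QT at or below 500 ms.

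**The case against.** The strongest objection is that this is a preference. Neither document makes QTcF above 500 ms a stopping criterion, and a summary category in a SAP need not match a dosing rule. The protocol says that it wrote study-specific rules deliberately, and it names the uncorrected interval. Its amendment summary says that Section 6.6 was revised to follow UK regulator recommendations on adverse reactions. That is fair as far as it goes. However, the summary does not mention the QT line, and neither document explains why only uncorrected QT is used.

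Second, other controls remain. "All recorded 12-lead ECGs will be reviewed by the Investigator, or qualified designee, and the review findings will be documented in the CRF" (Protocol 8.2.3.2), and abnormal tracings may lead to further recordings. The Investigator confirms on the first day of Period 2 that the subject can continue (Table 1 notes) and may withdraw a subject for safety (7.2). Immediate concerns go to the medical monitor (Section 8). The committee may evaluate study data and recommend dose changes or termination (4.1). It must meet within 24 hours of a treatment-emergent serious event or a withdrawal for an adverse reaction, and may meet ad hoc on urgent issues (8.4). So the harm arises only if a reviewed, drug-related QTcF above 500 ms prompts no action. This limits the severity, but none of these routes sets a QTcF limit.

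Third, the relevant readings are few. The Period 2 pre-dose ECG comes at least 14 days after dosing, when Protocol 4.2 expects more than 99.2% of plasma total Mo to be gone on average. Three readings per subject (4, 24 and 96 h) are more realistic than four for a drug effect. This stands.

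Fourth, adding QTcF leaves the early trigger below 60/min in place. That is true and intended: it keeps protection that the protocol already gives.

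Finally, the trigger estimate shows that false stops would be rare. It does not measure benefit. This also stands.

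**Conclusion.** The point holds as an optional, low-severity improvement. The gap follows from the wording of Section 6.6.1.1 and from the SAP's formula, and its limits need no outside data. How often a drug-related event would fall in the gap cannot be estimated from the documents. It should be rare: each subject receives two single 15 mg doses, and the two earlier studies at 60 mg showed no clinically important ECG trends (Protocol 2.2). The primary pharmacokinetic endpoint is not affected. The case for change rests on the judgement that a corrected interval belongs in a stopping rule when it is already planned as an ECG parameter.

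**What to change.** In Protocol 6.6.1.1, extend the QT line so that either measure triggers it, for example: *uncorrected QT above 500 ms, or QTcF above 500 ms, on a consistent and technically valid triplicate ECG*. The special group rules refer back to the individual rules and need no edit. SAP 4.11.3 needs no change.

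The edit is one line, but after approval it is probably a substantial amendment: the amendment summary lists the previous Section 6.6 change above its non-substantial revisions, and Protocol 10.1.1 requires ethics approval before a substantial change is implemented. It is best combined with another amendment if one is planned. QTcF must also be available when the Investigator reviews the safety ECG; Protocol 9.4.2 lists the parameter but, as an analysis section, does not say when it is ready. The cost in unnecessary stops is negligible under the assumptions above, and the triplicate requirement and the limit to drug-related reactions (6.6.1) reduce it further.
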